3.4. Justification of Dose

The dose of 15 mg/kg if body weight <13 kg, and 200 mg if body weight \geq 13 kg, TID was selected on the basis of clinical experience with vatiquinone and plasma concentration data in pediatric patients treated with doses of 100 to 200 mg TID. This dose range was well tolerated in all patients, showed biochemical evidence of target engagement, and was associated with clinical improvements in pediatric patients with mitochondrial disease. Using body weight-based dosing is standard of care for pediatric patients and eliminates the potential for overdose in low body weight patients, and also allows adequate plasma concentrations to be achieved in the face of significant variability in bioavailability.

3.5. End of Study Definition

The study will end when the last subject has completed the follow-up visit.

4. STUDY POPULATION

4.1. Overview

The study population consists of male and female subjects <21 years of age who have genetically determined mitochondrial disease and associated refractory epilepsy (defined as those who were unsatisfactorily treated with at least 2 antiepileptic drugs [AEDs]).

4.2. Inclusion Criteria

To be eligible for enrollment in the study, subjects must meet all of the following inclusion criteria:

1. Evidence of signed and dated informed consent/assent document(s) indicating that the subject (and/or his/her parent/legal guardian) has been informed of all pertinent aspects of the trial
2. Age <21 years at time of randomization
3. Subject or parent/legal guardian is able and willing to complete seizure diaries for the duration of the study
4. Subjects with genetic confirmation of inherited mitochondrial disease with associated epilepsy phenotype (Alpers/POLG, Leigh syndrome, MELAS), or other genetically confirmed mitochondrial diseases secondary to mitochondrial mutations (Pontocerebellar Hypoplasia Type 6 [PCH6], nuclear DNA RARS2 mutation) or myoclonic epilepsy with ragged red fibers (MERRF, mitochondrial DNA [mtDNA] mitochondrially encoded tRNA lysine [MT-TK] mutation) are eligible.
5. Despite treatment with at least 2 AEDs:
 - Have ≥ 6 observed motor seizures occurring during the 28 days prior to the Baseline Visit
 - Have ≥ 2 observed motor seizures in the first 14 days and ≥ 2 in the second 14 days of the Run-in period
 - Do not have a consecutive 20-day seizure free period and
 - Have at least 80% of seizure diary data
 - No changes to the AED regimen will be allowed (except weight-based dose adjustments) during the first 24-week period.
6. Documented medical history of epilepsy associated with mitochondrial disease for at least 6 months prior to screening except for subjects who are <2 years of age at the time of screening (subjects <2 years of age can be considered for enrollment if all other screening criteria are met due to the potential for rapid progression in these subjects).
7. Consent to abstain from non-approved therapies for 30 days prior to the Screening Visit and for the duration of the study
8. Stable dose regimen of antiepileptic therapies 30 days prior to the Screening Visit

9. Stable regimen of dietary supplements 30 days prior and, if on a ketogenic diet, stable ketogenic diet 90 days prior to the Screening Visit and for duration of the study
10. Electroencephalogram (EEG) at Screening or historical EEG up to 6 months prior to screening for diagnostic confirmation of epilepsy

4.3. Exclusion Criteria

Subjects will be excluded from enrollment if any of the following exclusion criteria apply:

1. Allergy to vatiquinone or sesame oil
2. Aspartate transaminase (AST) or alanine transaminase (ALT) $\geq 3 \times \text{ULN}$ at time of screening
3. INR $> \text{ULN}$ at time of screening
4. Serum creatinine $\geq 1.5 \times \text{ULN}$ at time of screening
5. Participation in another interventional clinical trial 60 days prior to randomization or for the duration of this clinical trial
6. Previously received vatiquinone
7. Concomitant treatment with drug(s) that have not received regulatory agency approval for the treatment of mitochondrial diseases and use of artisanal (non-Epidiolex cannabidiol) cannabidiol therapies
8. Concomitant treatment with idebenone
9. Ongoing treatment with strong cytochrome P450 (CYP) inhibitors such as itraconazole or strong CYP inducers such as rifampin. Treatment with these agents must be completed at least 4 weeks prior to enrollment. During the study, subjects should not use grapefruit/grapefruit juice or St John's wort extract.
10. Pregnant or lactating subjects or those male or female sexually active subjects who are unwilling to comply with proper birth control methods as defined in Section 7.5.10 from the time consent is signed until 30 days after treatment discontinuation. Females of childbearing potential must have a negative pregnancy test at Screening and during the Baseline Visit.
11. Comorbidities that may confound study results (eg, fat malabsorption syndrome, other mitochondrial disorders) in the opinion of the investigator.

4.4. Screen Failures

Any subject that does not meet inclusion or exclusion criteria within the defined screening window prior to randomization, will be considered a screen failure. Screen failures can be rescreened after consultation with the medical monitor.

4.5. Strategies for Recruitment and Retention

Subjects will be recruited via existing populations with mitochondrial diseases at identified investigational sites or via referrals.

4.6. Home Care Services

If for unforeseen reasons subjects are unable to travel to the study site, with approval from both the Principal Investigator and PTC medical monitor, they may be offered an opportunity to have study visits performed in their home.

In order to conduct the home visits, the subject must agree to utilize home care services. A licensed nurse will then contact the subject to schedule the visits.

The home care nurse, the home care agency, and the home care services provider may have access to the subject's personal data including their individually identifiable protected health information, such as the subject's name, address, or phone number. This type of information will only be used as necessary to schedule and conduct the home visits and will not be provided to the sponsor.

5. STUDY INTERVENTION

5.1. Study Intervention(s) Administration

5.1.1. Study Intervention Description

Vatiquinone oral solution is manufactured at 100 mg/mL for oral administration. Subjects will receive vatiquinone at a dose of 15 mg/kg if body weight <13 kg, and 200 mg if body weight \geq 13 kg, TID (Table 1). At each study visit the subjects are weighed; any change in weight of \geq 10% from baseline should result in dose adjustment. Weights ending in decimals \geq 0.5 should be rounded up to the next whole number for dosing calculation.

For this study, placebo will consist of sesame oil NF, with a colorant added to match vatiquinone oral solution. During the phase of the study where subjects are to receive placebo, a volume of placebo equal to the volume of active received when assigned to vatiquinone treatment will be provided to each subject.

Table 1: Weight-Based Dosing in mL of the 100 mg/mL Solution

Subject Weight (kg)	Dose (mg/kg) TID	Dose Volume (mL)
4	15	0.6
5	15	0.8
6	15	0.9
7	15	1.1
8	15	1.2
9	15	1.4
10	15	1.5
11	15	1.7
12	15	1.8
13	15	2.0
Above 13 kg	200 mg per dose	2.0

5.1.2. Dosing and Administration

Drug dosing will occur according to the schedule described in Sections 7.1.2 and 7.1.3. Food is required for appropriate absorption of vatiquinone from the gastrointestinal tract. For subjects who have a gastrostomy tube (G-tube) installed, the study drug will be instilled into the G-tube using an oral dispenser. For subjects who are receiving continuous feed with liquid nutritional preparation such as PediaSure, the feed is interrupted to allow instillation of the drug solution into the G-tube using an oral dispenser, followed by resumption of the continuous feed to flush the drug into the stomach. For subjects who received G-tube feeding as bolus, the study drug is instilled into the G-tube using an oral dispenser, followed by the feed bolus to flush the drug into the stomach. The same procedures are to be followed in case the subject has a nasogastric tube installed. Additional detail on dosing can be found in the Pharmacy Manual.

For subjects who do not have a G-tube installed and who can swallow, the study drug is given orally using an oral dispenser along with a meal that includes foods such as cream cheese, peanut butter, or other fatty components. The dose of study drug needs to be followed by eating yogurt, ice cream (no non-fat), or any other food with at least 25% calories from fat.

5.1.3. Treatment of Missed Doses

If a dose is missed, or if the subject vomits after receiving a dose, the dose should not be “made up.” The subject will be required to skip that dose and wait until the next scheduled dose.

5.2. Preparation/Handling/Storage/Accountability

5.2.1. Accountability

Adequate records of study drug receipt and disposition will be maintained by the (Institution’s) Pharmacy Records of receipts, investigational drug orders, dispensing records, and disposition forms. The study monitor will assess drug accountability and will request to review the Pharmacy Records and investigator study file to assure the study medication is prescribed by the investigator or designee for the purpose of this study.

At study completion, all drug supplies including partially used and empty containers must be either returned to the sponsor or designee or destroyed per your institution’s guidelines for destruction of investigational product after drug accountability has been performed by the study monitor.

5.2.2. Formulation, Appearance, Packaging, and Labeling

Vatiquinone oral solution, 100 mg/mL, is a solution of vatiquinone drug substance in super refined, preservative free sesame oil. At room temperature, it is a yellow to orange clear liquid. Fifty-four mL of the solution is filled into a 60 mL amber glass bottle and closed with child resistant cap suitable for multiple dose administration. The placebo oral solution is packaged in the same container/closure as the active substance and is also a yellow to orange clear liquid.

Each bottle will be labeled with the following but not limited to: Product name, concentration, batch number, expiration date, storage conditions, and a caution limiting it for Clinical Trial Use Only.

5.2.3. Preparation

No preparation is required; vatiquinone is provided as a ready-to use oral solution.

5.3. Measures to Minimize Bias: Randomization and Blinding

Subjects meeting the eligibility criteria for the randomized placebo-controlled phase will be randomized at the Baseline Visit to either vatiquinone treatment or placebo group. Subjects who withdraw from the study after being assigned a subject number will retain that subject number. Randomization will be stratified by disease subtype including: 1) Alpers/POLG, 2) Leigh syndrome, 3) MELAS, and 4) Other genetically confirmed mitochondrial disease secondary to either nuclear or mitochondrial DNA mutation.

The investigators, study subjects, and sponsor will be blinded as follows: the sponsor will be blinded to the randomized treatment until the study is unblinded after all subjects complete the placebo-controlled phase; subjects and investigators remain blinded to the treatment received during the placebo-controlled phase until after all subjects complete the open-label phase. An independent Data Safety Monitoring Board (DSMB) will monitor the study until completion of the placebo-controlled phase of the study.

Under normal circumstances, the blind will not be broken. The blind may be broken by the principal investigator only if specific emergency treatment would be dictated by knowing the treatment assignment. The investigators have the ability to unblind via the Interactive Response Technology system.

5.4. Study Intervention and Compliance

Study medication will be reviewed to assess compliance on an ongoing basis. Subjects who take >80% of the prescribed doses and no more than 120% of the prescribed doses will be considered compliant. Subjects who fall outside of this threshold will be counseled and instructed on dosing procedures. Medication compliance will be recorded in the diary.

5.5. Concomitant Therapy

Any medication taken by a subject 30 days prior to Baseline Visit and during the course of the study and the reason for use of the medication will be recorded on the electronic case report form (eCRF)/paper case report form (CRF). During Screening, each subject will be instructed to report the use of any medication to the investigator. Subjects will also be instructed about the importance of not taking any medication throughout the study (including over-the-counter medications) without consulting the investigator.

All immunizations will be considered as concomitant medications and will be recorded in the CRF. Subjects will be instructed to consult the investigator before immunization. The final decision on any immunization should be made by the treating physician in consultation with the patient and/or caregiver.

6. STUDY INTERVENTION DISCONTINUATION AND PARTICIPANT DISCONTINUATION/WITHDRAWAL

6.1. Discontinuation of Study Intervention

Subjects receive study treatment until treatment discontinuation for one of the reasons listed below. However, subjects may discontinue study treatment or withdraw their consent to participate in the study at any time without prejudice.

The following conditions require subject discontinuation from all study treatment:

1. At their own request or at the request of their legally authorized representative
2. If a subject experiences an AE that is deemed related to treatment with vatiquinone and, in the investigator's or the sponsor's medical judgment, continuation of treatment would be detrimental to the subject
3. Spontaneous bleeding in a subject
4. At the specific request of a regulatory agency for termination of treatment of an individual subject or all subjects under the protocol
5. Subject participation in another clinical study using an investigational agent or investigational medical device
6. Refusal of sexually active fertile subjects (excluding subjects who have been sterilized) to use medically accepted methods of contraception (Section [7.5.10](#))
7. If a subject becomes pregnant
8. Significant noncompliance with the protocol in the opinion of the investigator or the sponsor
9. Use of prohibited concomitant medication

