7.1.9. Prohibited Medications

Subjects will be required to maintain a stable regimen of mitochondrial disease supplements from screening throughout the trial.

Anticoagulants such as vitamin K antagonists, Factor Xa inhibitors are not permitted during the course of the study because of the potential interaction with vatiquinone on vitamin K associated coagulation factor synthesis.

Cytochrome P450 inhibitors such as itraconazole have been demonstrated to significantly increase the plasma concentrations of vatiquinone (up to 2-fold). Cytochrome P450 inducers such as rifampin significantly reduce the plasma concentrations of vatiquinone (up to 50% less). Therefore, strong CYP inducers and inhibitors, including grapefruit/grapefruit juice and St John's wort extract, should be avoided during the course of the study.

- In case treatment with a CYP inhibitor is required during the course of the study, coagulation parameters should be monitored and vatiquinone dose should be reduced by 33% in case INR increases over 1.5×ULN or Common Terminology Criteria for Adverse Event (CTCAE) Grade 2.
- In the event that a CYP inducer is used, no adjustment of the study drug dose will be required because there are no safety concerns with CYP inducers.

No changes to the AED regimen (except for weight-based dose adjustments) will be allowed during the first 24-week period.

The use of artisanal (non-Epidiolex cannabidiol) cannabidiol therapies should continue to be excluded due to uncertainty regarding the quality and quantity of cannabidiol in the artisanal product.

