APPENDIX 1. PTC743-MIT-001-EP PROHIBITED MEDICATION LIST

Table 7: PTC743-MIT-001-EP Prohibited Medication List

Prohibited Medications	Examples
Anticoagulants	
 • heparin • warfarin • aspirin • clopidogrel • apixaban • dabigatran • edoxaban • enoxaparin • rivaroxaban
CYP3A4 strong inducers	
 • apalutamide • carbamazepine • enzalutamide • mitotane • phenytoin • rifampin • St. John's wort
CYP3A4 strong inhibitors	
 • boceprevir • cobicistat • danoprevir and ritonavir • elvitegravir and ritonavir • grapefruit juice (any grapefruit product) • indinavir and ritonavir • itraconazole • ketoconazole • lopinavir and ritonavir • paritaprevir and ritonavir and (ombitasvir and/or dasabuvir) • posaconazole • ritonavir • saquinavir and ritonavir • telaprevir • tipranavir and ritonavir • telithromycin • troleandomycin • voriconazole • clarithromycin • idelalisib • nefazodone • nelfinavir
Investigational medications for MIT-E	
Idebenone	

Prohibited Medications	Examples
Artisanal (non-Epidiolex cannabidiol)	

Abbreviations: CYP3A4, cytochrome P450 3A4

Note: This list is neither comprehensive, nor final. In general, study subjects should not be taking any strong CYP3A4 inhibitors or inducers, anticoagulants, or any investigational medications.

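### The protocol gives two conflicting safety rules: stop or continue study drug on a prohibited CYP agent, and Grade 1 or Grade 2 as the day-14 INR threshold

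*Protocol*

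**What the plan says.** **CYP agents.** Protocol 6.1 introduces its list with "The following conditions require subject discontinuation from all study treatment". Item 9 reads "Use of prohibited concomitant medication" and carries no exception. Exclusion criterion 9 in section 4.3 bars "Ongoing treatment with strong cytochrome P450 (CYP) inhibitors such as itraconazole or strong CYP inducers such as rifampin". The note to the Appendix 1 list of prohibited medications says "In general, study subjects should not be taking any strong CYP3A4 inhibitors or inducers".

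Section 7.1.9, which is headed as the section on prohibited medications, gives the pharmacological reason: "Cytochrome P450 inhibitors such as itraconazole have been demonstrated to significantly increase the plasma concentrations of vatiquinone" (up to 2-fold), while inducers such as rifampin lower them by up to 50%. It asks that "strong CYP inducers and inhibitors, including grapefruit/grapefruit juice" and St John's wort be avoided. Two bullets then cover what to do if such drugs are used:

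- Inhibitor: "In case treatment with a CYP inhibitor is required during the course of the study, coagulation parameters should be monitored", with a 33% dose cut if INR rises above 1.5×ULN or CTCAE Grade 2.
- Inducer: "In the event that a CYP inducer is used, no adjustment of the study drug dose will be required".

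**INR.** In section 7.4.6, a drug-related INR of Grade 2 or above (over 1.5×ULN) triggers a reduction to 66% of dose. The text then permits a further reduction or discontinuation if INR has not come down to Grade 1 within two weeks, and it cites Table 3. The last column of Table 3, as extracted, applies when INR has not come down to Grade 2 or lower after 14 days. Its action is to consider withdrawal after consulting the medical monitor.

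**Related wording.** Section 1.5.1 commits to adjusting or stopping study drug if PT or PTT exceeds 1.5×ULN. Protocol 2.2.4.2 and SAP 1.3.4.3 describe PTT as reported in INR units.

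**The concern.** Section 1.4.1 identifies anticoagulation as the dose-limiting effect in both rat and dog, so this is the risk for which sites most need a single instruction.

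As written, a subject who needs itraconazole must stop study drug under 6.1. Under 7.1.9 the same subject stays on full dose, with plasma concentrations up to doubled, until INR passes 1.5×ULN. Two sites could do opposite things and both cite the protocol.

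The situation is plausible in this population. The strong inducers in Appendix 1 include carbamazepine and phenytoin, both antiepileptics. Changes to the antiepileptic regimen are barred only for the first 24 weeks, and vatiquinone dosing then continues for 48 weeks in the extension. Section 5.3 has the DSMB monitoring only until the placebo-controlled phase is complete, so in the extension sites rely more on the written rule.

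For INR, a site working from Table 3 finds no step for a Grade 2 value at day 14, while a site working from the paragraph above it does.

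**Working it through.** No sample size, power or alpha figure is involved. The check is a comparison of current protocol text, plus simple dose arithmetic.

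**1. Do the 7.1.9 bullets cover prohibited drugs?** The bullets say inhibitor and inducer without the word *strong*. The agents named in the paragraph that introduces them are:

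| Agent named in 7.1.9 | Appendix 1 list |
|---|---|
| Itraconazole | Strong inhibitor |
| Grapefruit | Strong inhibitor |
| Rifampin | Strong inducer |
| St John's wort | Strong inducer |

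That is 4 of 4. Exclusion criterion 9 itself gives itraconazole and rifampin as examples of strong agents. The natural reading is that the bullets apply to prohibited drugs.

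**2. What dose does each rule give?** For a subject of 13 kg or more assigned to vatiquinone:

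- Full dose: 3 × 200 = 600 mg/day.
- After the reduction from three to two doses a day (Table 3): 2 × 200 = 400 mg/day, and 400/600 = 66.7%. This agrees with the 66% in the 7.4.6 text and, to rounding, with the 33% cut in 7.1.9, so the first reduction step is consistent throughout.

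| Situation | 6.1 item 9 | 7.1.9 |
|---|---|---|
| Strong inhibitor, INR not above 1.5×ULN | 0 mg/day | 600 mg/day |
| Strong inhibitor, INR above 1.5×ULN | 0 mg/day | about 400 mg/day |
| Strong inducer | 0 mg/day | 600 mg/day |

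**3. Day-14 INR, grade by grade.**

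| INR grade at day 14 | 7.4.6 text | Table 3 |
|---|---|---|
| 1 or below | Resolved | Resolved column: stay at 2/3 dose |
| 2 | Further reduce or discontinue | No column applies |
| 3 or above | Further reduce or discontinue | Consider withdrawal |

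Grade 2 is too high for the resolved column and too low for the non-resolved one. Because the rule starts at Grade 2, a subject who enters at Grade 2 and does not improve never reaches the last column. That column also leaves out the further reduction that the text allows.

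**4. Coagulation parameters.** Section 1.5.1 names two, PT and PTT. Section 7.4.6 and Table 3 carry only an INR trigger, which covers PT, so 1 of 2 (PTT) has no specific rule. Sections 7.4.2.2 and 7.4.5 attach INR to PT only, which shows that the unit wording in Protocol 2.2.4.2 and SAP 1.3.4.3 is a slip.

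**The case against.** **The CYP clauses can be reconciled.** Appendix 1 and exclusion criterion 9 restrict *strong* agents, while the 7.1.9 bullets do not use that word. If they cover only weaker agents, item 9 is not engaged. Alternatively, the specific rule for a medically required inhibitor qualifies the general one. The amendment history shows that Version 4.1 added both item 9 and the inducer guidance, which suggests they were meant to coexist. Either reading is possible, but the two lead to opposite actions for itraconazole and neither is stated. The narrow reading also sits badly with the four agents named just before the bullets.

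**The safety margin is wide.** Section 1.4.1 puts 17,800 ng/mL at about 16 times Cmax at the highest clinical dose of 400 mg, so Cmax is about 17,800/16 ≈ 1,113 ng/mL. Doubling gives about 2,225 ng/mL, against NOAEL values of 8,828 (rat) and 12,854 (dog): margins of 8,828/2,225 ≈ 4.0 and 12,854/2,225 ≈ 5.8. This is indicative only, because the section gives neither the regimen nor paediatric exposure. Section 1.4.2 also reports no coagulation changes deemed associated with the drug, subjects with INR above ULN at screening are excluded, and spontaneous bleeding is itself a stopping criterion. These points stand. They lower the expected harm but do not tell a site which rule to follow.

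**The INR mismatch changes no mandatory action.** Table 3 is labelled as example guidance, both second steps are discretionary, the governing text does cover Grade 2, and the investigator is responsible for dose decisions. This also stands and limits the severity. The two thresholds still differ, and the table appears to be the one in error.

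**PTT is not unmanaged.** It is monitored, and clinically significant abnormalities can lead to dose changes through the adverse event provisions. For that reason it is treated here as minor.

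**Conclusion.** Both conflicts are present in the current Version 8.0 text and should be fixed.

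- **CYP rule:** a mandatory stop against continued dosing, with no statement of precedence. This assumes that the 7.1.9 bullets reach strong agents, as the surrounding paragraph indicates. If they do not, the text needs to say so. The wording of 6.1 is mandatory, so investigator discretion does not soften this conflict.
- **INR rule:** one grade, Grade 2 at day 14, is actionable in the text and absent from the table. This assumes that the extracted column header matches the original.
- **Minor:** PTT has a commitment in 1.5.1 but no trigger in 7.4.6, and its unit is misdescribed in both documents.

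The documents give no frequency for either situation, and cases may be few. The consequence is inconsistent safety management across sites. No effect on the primary analysis is claimed.

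**What to change.** 1. Add to 6.1 item 9 an exception for CYP inhibitors or inducers managed under 7.1.9. If discontinuation is what is intended, limit the two 7.1.9 bullets to agents that are not strong. Under either option, item 9 stays in force for anticoagulants, idebenone and artisanal cannabidiol.
2. Change the last column of Table 3 so that it applies when INR has not resolved to Grade 1 or lower after 14 days, and add further dose reduction as an option there, to match the text.
3. Minor: either add the PTT trigger of 1.5×ULN to 7.4.6 or remove PTT from 1.5.1. Correct Protocol 2.2.4.2 and SAP 1.3.4.3 so that INR refers to PT only.

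The choice between stopping and continuing on a strong CYP agent belongs to the medical team and the DSMB. The cost is low: a few wording changes in the protocol and one in the SAP, with no change to sample size or any efficacy analysis.
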